## **Primary Outcome**

Incidence rate/100 patient years for both severe hypoglycemia (SH) and diabetic ketoacidosis (DKA).

**Success Criteria/Goal:** Study participants will not experience a higher incidence of SH or DKA than incidence rates reported in the literature from analyses of similar populations. Overall outcomes will be compared to data below, derived from a recently published study using a large Type 1 Diabetes Exchange cohort (Foster et al., 2019). This study used a similar design as our postmarket study proposed here, the subjects represent our intended use population, and the event rates reported in the Foster study fall within the broader rates found in the extensive body of literature reviewed.

SH Incidence Rates (all ages)		SH Incidence Rates in Children			SH Incidence Rates in Adults	
All ages (13-93)			Ages 6-12	Ages 13-17	Ages 18-93	
All insulin delivery	25/100 PY	All insulin delivery	22/100 PY	20/100 PY	All insulin delivery	30/100 PY
MDI	37/100 PY	MDI	28/100 PY	34/100 PY	MDI	38/100 PY
IPT	23/100 PY	IPT	16/100 PY	13/100 PY	IPT	27/100 PY
DKA Incidence Rates (all ages)		DKA Incidence Rates in Children			DKA Incidence Rates in Adults	
All ages (13-93)			Ages 6-12	Ages 13-17	Ages 18-93	
All insulin delivery	11/100 PY	All insulin delivery	13/100 PY	14/100 PY	All insulin delivery	9/100 PY
MDI	17/100 PY	MDI	22/100 PY	25/100 PY	MDI	13/100 PY
IPT	7/100 PY	IPT	5/100 PY	9/100 PY	IPT	7/100 PY

The full literature review can be found in Attachment 1 of this protocol.

The safety of automatically populating CGM readings into the bolus calculator will be analyzed by correlating reported AEs, calculator usage data and CGM readings to understand if the bolus calculator may have caused the AE. This analysis will isolate AEs where three consecutive CGM readings  $\leq 54$  mg/dL, or  $\geq 250$  mg/dL existed within five hours of receiving a correction bolus using an automatically populated CGM reading. All CGM readings within 5 hours after the bolus is given will be evaluated. In addition, correction boluses using automatically populated CGM values  $\geq 250$  mg/dL will be analyzed and evaluated separately from boluses given for lower glucose values.

Secondary endpoints will be calculated as means/medians as appropriate based on data extracted from the Tandem t:connect web application and patient reported outcomes. Sensor-glucose concentrations will be analyzed per recent international consensus guidelines, to include time in target range 70-180 mg/dL, time  $> 180$  mg/dL, time  $> 250$  mg/dL, time  $< 70$  mg/dL, time  $< 54$  mg/dL.

Outcomes will be analyzed quarterly and tabulated using standard statistical tools such as SPSS, R and Python.

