### **Study Endpoints**

- Primary Safety Endpoints: Composite rate of severe hypoglycemia and diabetic ketoacidosis through 12 months following initiation of therapy with the Control-IQ System.
- Secondary Effectiveness Endpoints
  - Glycemic outcomes (based on data from CGM sensor values):
    - % time in range (70-180 mg/dL)
    - % time <54 mg dL
    - % time <70 mg/dL
    - % time >180 mg/dL

- %time >250 mg/dL
- Patient-reported outcomes:
  - Satisfaction with device
  - Trust in the system
  - Usability of the system
  - Sleep quality

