### **Subject Withdrawal or Termination**

Subjects are free to withdraw from the study at any time and will be withdrawn if they inform Tandem that they no longer wish to participate. Data collected prior to the subject's withdrawal will remain part of the study record and will be included in the analyses. All participants that have been successfully enrolled in the study will receive regular invitations to provide data. A Retention Management protocol will be initiated to attempt to re-engage participants that do not respond after three separate outreach attempts.

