#### *Step 1 – Power analysis for severe hypoglycemia (SH)*

An overall incidence rate of 25.35 events per 100 patient years (PY) was used in the power analysis for severe hypoglycemia. We calculated that a sample size of 1,354 individuals with T1D would provide 80% power with a type 1 error rate (two-sided) of 5% to detect a difference, if there is one, between the expected SH rate (25.35) and the proposed study sample SH event rate.

A separate power analysis for the 14-18 age group used an overall SH incidence rate of 19.5 events/100PY. Results indicated that a sample size of 231 individuals with T1D between the ages of 14-18 would provide 80% power with a type 1 error rate (two-sided) of 5% to detect a difference, if there is one, between the expected SH rate (19.5) and the proposed study sample SH event rate. Of the overall sample of 1,354 subjects, at least 231 subjects will be 14-18 years old to provide sufficient power to detect risk of SH in this younger age group.

A separate power analysis for the 6-13 year old group used a SH incidence rate of 21.9 events/100PY, which is a weighted average of both MDI and pump users (since pump users were overrepresented in this age group). Results indicated that a sample size of 288 individuals with T1D between the ages of 6 and 13 would provide 80% power with a type 1 error rate (two-sided) of 5% to detect a difference, if there is one, between the expected SH rate (21.9) and the proposed study sample SH event rate. In addition to

the overall sample, at least 288 subjects will be 6-13 years old to provide sufficient power to detect risk of SH in this younger age group. *Step 2 – Power analysis for diabetic ketoacidosis (DKA)*

An overall incidence rate of 11.03 events per 100 patient years was used in the power analysis for DKA . We calculated that a sample size of 1,282 individuals with T1D would provide 80% power with a type 1 error rate (two-sided) of 5% to detect a difference, if there is one, between the expected DKA rate (11.03/100 PY) and the proposed study sample DKA event rate.

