A separate power analysis for the 14-18 age group used an overall DKA incidence rate of 14.2 events/100PY. Results indicated that a sample size of 328 individuals with T1D between the ages of 14-18 would provide 80% power with a type 1 error rate (two-sided) of 5% to detect a difference, if there is one, between the expected DKA rate (14.2) and the proposed study sample DKA event rate. Of the overall sample of 1,282 subjects, at least 328 subjects will be 14-18 years old to provide sufficient power to detect risk of DKA in this younger age group.

A separate power analysis for the 6-13 year old group used an overall DKA incidence rate of 13.2 events/100PY, which is a weighted average of both MDI and pump users (since pump users were overrepresented in this age group). Results indicated that a sample size of 77 individuals with T1D between the ages of 6-13 would provide 80% power with a type 1 error rate (two-sided) of 5% to detect a difference, if there is one, between the expected DKA rate (13.2/100PY) and the proposed study sample DKA event rate. In addition to the previously determined sample, at least 77 subjects will be 6-13 years old to provide sufficient power to detect risk of DKA in this younger age group.

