## **Statistical Analysis**

Descriptive statistics will be used to describe outcomes vs. a comparator group. The Comparator Group will be determined using evidence from a systematic literature review examining MDI, insulin pump therapy (IPT) and sensor augmented pump (SAP) use in patients with type 1 diabetes. Studies published since January, 2020 will be included in the analysis. This will establish the baseline sample representation and outcome metrics. Users of automated dosing systems, including low glucose suspend, predictive low glucose suspend (such as Basal-IQ technology) will not be analyzed as part of the Comparator group.

The publications included in the literature review have been identified to represent the typical population of people with type 1 diabetes, and include sample populations that mirror those described above in the target population for this study, including:

- Children age 6 years old and older
- Adolescents age 14-18 years old
- Adults >18 years old
- Patients with pump experience
- Pump naïve patients
- Patients with CGM experience
- CGM naïve patients
- Wide range of baseline HbA1c values

Primary endpoints, the risk of AE (DKA, SH), represented as risk ratio per 100 patient years, will be compared using a single sample two-tailed exact binomial test (alpha=0.05) to the expected values as extracted in the literature review. Effect size will be defined as the absolute difference in risk ratios.

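### Success is defined as SH and DKA rates that are not higher than the literature, but the only test is one of difference, no rule says which result is success, and the Study Endpoints section names a composite instead

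*Combined protocol and SAP*

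**What the plan says.** - **Goal.** The success criterion in the Primary Outcome section reads: "Study participants will not experience a higher incidence of SH or DKA than incidence rates reported in the literature from analyses of similar populations". The same section adds "Overall outcomes will be compared to data below", followed by a table of rates from one published registry cohort.
- **Test.** The synopsis and the Statistical Analysis section both give a "single sample two-tailed exact binomial test (alpha=0.05") against the expected literature values. Effect size is defined only as a scale, with no number.
- **Power.** Determination of Sample Size, Step 1, sizes the study for 80% power "to detect a difference, if there is one, between the expected SH rate (25.35) and the proposed study sample SH event rate". Step 2 uses parallel wording for DKA. Neither step states an alternative rate or a direction.
- **Endpoint.** Study Endpoints gives the primary safety endpoint as "Composite rate of severe hypoglycemia and diabetic ketoacidosis through 12 months following initiation of therapy with the Control-IQ System". Primary Outcome gives it as "Incidence rate/100 patient years for both severe hypoglycemia (SH) and diabetic ketoacidosis (DKA").
- **Deferred detail.** Determination of Sample Size promises a detailed statistical analysis plan, to be finalized before data are first tabulated. That plan is not part of the document.
- **Exposure.** Subject Withdrawal or Termination: "Data collected prior to the subject's withdrawal will remain part of the study record and will be included in the analyses".

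**The concern.** The primary objective is to demonstrate safety. The error to limit is therefore a conclusion of not higher when the true rate is higher. A test of difference controls the opposite error, that of declaring a difference when there is none. A non-significant result from such a test shows only that the data did not establish a difference, and it becomes more likely as exposure falls. Without a written rule, the same data could be reported as success or as no conclusion.

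The endpoint wording adds a second ambiguity. A single composite rate and two separate rates can lead to different conclusions, because SH is the more frequent event and can outweigh DKA in a sum.

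**Working it through.** **Inputs.** Benchmarks are 25.35 (SH) and 11.03 (DKA) per 100 patient-years, from Determination of Sample Size; the Primary Outcome table shows them as 25 and 11. Alpha is 0.05 two-sided. Expected completers are 1,547 in the synopsis and 1,354 in Step 3.

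**1. The plan's own figures.** 2,063 × 0.75 = 1,547 reproduces the synopsis. The 1,354 in Step 3 does not follow from 2,063 and 25% attrition, since 1,354 / 0.75 = 1,805. The sizes 1,354 (SH) and 1,282 (DKA) cannot be reproduced because no alternative p1 is given. They can be solved backwards from

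n = [1.96·√(p0(1−p0)) + 0.842·√(p1(1−p1))]² / (p1−p0)².

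- SH, p0 = 0.2535, n = 1,354: p1 = 28.7 per 100 (ratio 1.13) or 22.1 (ratio 0.87).
- DKA, p0 = 0.1103, n = 1,282: p1 about 13.6 (ratio 1.23) or 8.7 (ratio 0.78).

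Both directions fit, so the sizes do not show which was intended.

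**2. Chance of passing if success means not significantly higher.** Let c be the smallest count with P(X ≥ c | p0) ≤ 0.025. The pass probability is P(X ≤ c−1) at the true rate p0 × f. The binomial version assumes one patient-year and at most one event per subject. The Poisson version allows repeat events and uses mean 1,547 × p0 × f. At 1,547, c for SH is 427 (binomial) or 432 (Poisson), and for DKA 196 or 198.

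| True rate | Binomial | Poisson |
|---|---|---|
| DKA 10% above | 73.0% | 76.5% |
| DKA 20% above | 24.5% | 30.9% |
| SH 10% above | 39.2% | 50.5% |
| SH 15% above | 8.5% | 18.0% |

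Exposure matters moderately. Pre-withdrawal data are kept, so if each of the 516 dropouts contributes half a year (an assumption), exposure is 1,547 + 516 × 0.5 = 1,805 patient-years. From 1,805 down to 1,354, and across both models, DKA 20% above passes 19.5 to 36.6% and SH 10% above passes 32.3 to 56.3%. Less data makes passing easier.

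The largest binomial DKA count that passes is 195 of 1,547. That is 12.6 per 100, or 14% above benchmark. Its exact 95% interval is 11.0 to 14.4, and the upper end is 30% above (14.4 / 11.03 = 1.30).

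**3. Three possible readings of success.** Binomial, n = 1,547:

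| Reading | SH at benchmark | DKA at benchmark | DKA 20% above |
|---|---|---|---|
| Not significantly higher | 97.7% | 97.7% | 24.5% |
| Observed rate at or below benchmark | 51.0% | 50.0% | 0.4% |
| Significantly lower | 2.4% | 2.3% | under 0.1% |

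**4. Composite, as illustration only.** No composite benchmark is stated, so assume the sum: 25.35 + 11.03 = 36.38 per 100 patient-years. With DKA 20% above and SH 10% below, the true composite is 1.20 × 11.03 + 0.90 × 25.35 = 13.24 + 22.82 = 36.05. At 1,547 patient-years (Poisson, upper rejection count 611) it passes as not significantly higher 98.6% of the time. DKA tested alone would be flagged 69.1% of the time.

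**The case against.** Several objections carry weight.

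- **The rule may be in the later plan.** This stands as a limit on the finding: the gap is shown for this document only. A reader might infer that the rule would be chosen after the rates are seen. The document does not support that, because it requires the detailed plan to be final before the first tabulation. Even so, the success criterion is already written in the protocol, and the endpoint conflict has to be corrected there.
- **The upper tail of the test covers the goal, with 80% power.** A two-tailed test can show a higher rate, and a significantly lower rate would validly support the goal, so two-sidedness is not the fault. But the document does not say that absence of upper-tail rejection is success, and the 80% applies only at an alternative rate it does not give.
- **The pass rates rest on one inferred reading.** This stands. Under the point-estimate reading, DKA 20% above passes only 0.4% of the time. The missing rule is certain; the harm depends on how it is filled.
- **Whether both events must succeed is already clear.** One might infer that this is open. In ordinary English, the stated goal means that neither SH nor DKA may be higher.
- **Age-group claims.** One might infer that ages 6–13 and 14–18 carry their own success claims, since they are powered separately. The criterion compares overall outcomes, so age-group pass rates would attach to a claim the plan may not make.
- **A rule that accepts only lower would impose superiority.** This stands. It would replace the sponsor's goal, so it is not proposed as the success criterion.

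**Conclusion.** The concern holds in limited form. The goal is one of not higher, the only stated method tests for a difference, and the document does not link a result to success. The likely-to-be-inferred reading, not significantly higher, would not demonstrate the goal: at 1,547 patient-years it lets through DKA 20% above benchmark about a quarter to a third of the time, and SH 10% above about 39 to 51%. The protection is much better for overall SH at 15% above or more (8.5 to 18.0% pass). These figures assume the overall benchmarks are exact, although the plan itself reports very wide literature ranges (0–100 for SH and 0.4–26 for DKA per 100 patient-years).

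The composite wording in Study Endpoints is inconsistent with the sample-size, Statistical Analysis and Primary Outcome sections, and needs correcting whichever rule is chosen. A reader might go further and infer that the study will hide a DKA increase inside a composite. That is not supported: no section plans a composite test or gives a composite benchmark. The data remain usable; what needs repair is the link from result to conclusion.

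**What to change.** 1. In Study Endpoints, replace the composite with two separate rates, SH and DKA, matching Primary Outcome. State that neither may be higher than its benchmark.
2. In the synopsis, Statistical Analysis and Primary Outcome, report each as events per 100 patient-years with a two-sided 95% confidence interval, by a named method consistent with the test.
3. State that a non-significant result alone does not establish not higher. Conclude higher if the lower limit exceeds the benchmark and lower if the upper limit is below it. Otherwise report the result as inconclusive, with the interval shown.

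If the sponsor wants a positive not-higher claim for a device at about the benchmark rate, it needs a non-inferiority margin fixed before outcome data are seen. That choice, and any success claim by age group, belongs to the sponsor and is not part of this change.

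**Cost.** No added subjects, contacts or data. The downside is fewer positive claims. At 1,547, a device exactly at benchmark would be inconclusive about 95% of the time per endpoint (binomial 95.3% for each). One truly 10% better would be shown lower 63.4% (SH) and 27.6% (DKA) of the time under the binomial, or 51.5% and 26.0% under the Poisson.

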## PROTOCOL SYNOPSIS

Protocol Number	V07
Protocol Title	Control-IQ Observational (CLIO) US Post-Approval Study
Device	t:slim X2 insulin pump with Control-IQ technology (Control-IQ System)
Type of Protocol	Post Approval Study
Rational	
This post-approval study is primarily designed to collect safety data on this US FDA-cleared product. Several secondary endpoints assessing the effectiveness of this product in real-world use will also be collected. The t:slim X2 insulin pump with Control-IQ technology will be used as intended and in accordance with FDA-approved labeling.

Objectives	
Primary objective: To demonstrate, in a real-world setting, the safety of the Control-IQ System for the management of type 1 diabetes by assessing the rate of severe hypoglycemia (SH) and diabetic ketoacidosis (DKA).
 
Secondary objective: To demonstrate, in a real-world setting, the effectiveness of the Control-IQ System for the management of type 1 diabetes by assessing the impact on patients' glycemic outcomes and user experience in the real world, during the first 12 months of use.

Primary Endpoints	
Safety Endpoints:
 
 
1) The incidence rates of severe hypoglycemia (SH) and diabetic ketoacidosis (DKA), and
 
2) The safety of the automatic population of CGM readings into the bolus calculator of the Control-IQ System
 
 
Secondary Endpoints:
 
 
3) To determine glycemic outcomes as a measure of efficacy of the Control-IQ System, and
 
4) To demonstrate patient-reported satisfaction with and trust in the Control-IQ System, usability of the system, and sleep quality.
 

Duration of Study	All enrolled subjects will be monitored for outcome data for 12 months after starting the Control-IQ System.
Study Design	This post-approval study is a single-arm, prospective study. It is designed to assess 12-month safety in a real-world setting, and to support the continued assessment of the Control-IQ System for the treatment of type 1 diabetes in the United States. In addition, data will be collected to assess glycemic outcomes and user experience.

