Statistical Analysis	
Descriptive statistics will be used to evaluate outcomes vs. a comparator group. The Comparator Group will be determined using evidence from a systematic literature review examining MDI, insulin pump and sensor augmented pump (SAP) use in patients with type 1 diabetes. Primary endpoints, the risk of AE (DKA, SH), represented as risk ratio per 100 patient years, will be compared using a single sample two-tailed exact binomial test (alpha=0.05) to the expected values as extracted in the literature review. Effect size will be defined as the absolute difference in risk ratios. The safety of automatically populating CGM readings into the bolus calculator will be analyzed by correlating reported AEs, calculator usage data and CGM readings to understand if the bolus calculator may have caused the AE. This analysis will isolate AEs where three consecutive CGM readings <math>\leq 54</math> mg/dL, or <math>\geq 250</math> mg/dL existed within five hours after a correction bolus was given using an automatically populated CGM reading. Boluses using automatically populated CGM values <math>\geq 250</math> mg/dL will be analyzed and evaluated separately from boluses given for lower glucose values.
 
Secondary endpoints will be calculated as means/medians as appropriate based on data extracted from the Tandem t:connect web application and patient reported outcomes. Sensor-glucose concentrations will be analyzed per recent international consensus guidelines, to include time in target range 70-180 mg/dL, time <math>> 180</math> mg/dL, time <math>> 250</math> mg/dL, time <math>< 70</math> mg/dL, time <math>< 54</math> mg/dL.
 
Outcomes will be analyzed quarterly and tabulated using standard statistical tools such as R and Python.

----------------------	--

The study will be conducted and documented in accordance with the US Federal and Local requirements for post-market human clinical studies, the protocol, and the stipulations of the clinical trial agreement.

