### **General Description of Investigational Device**

The t:slim X2 insulin pump with Control-IQ technology, the hybrid closed-loop insulin delivery system from Tandem Diabetes Care, is intended for subcutaneous delivery of insulin for the management of type 1 diabetes mellitus. The system uses advanced closed-loop control algorithms to adjust insulin delivery to help keep blood glucose in a targeted range. The current Control-IQ System components include the t:slim X2 insulin pump with Control-IQ technology and the current generation of the Dexcom G6 CGM.

Future iterations of the Control-IQ System may incorporate FDA-cleared modifications to the algorithm and integration with any FDA-cleared continuous glucose monitors that meet the iCGM criteria. Subjects in this study will be allowed to update their therapy with future products from Tandem Diabetes Care, Inc., and future FDA-cleared CGMs that meet the iCGM criteria, during the study period.

The Control-IQ Technology uses data from the CGM and other inputs to:

- decrease and/or suspend insulin delivery when hypoglycemia is predicted (or occurs);
- increase insulin delivery when hyperglycemia is predicted (or occurs), and
- deliver automated correction boluses when necessary to mitigate hyperglycemia

The system used in this study is comprised of a CGM sensor and transmitter along with an insulin pump with user interface (IU) for display of system information, and a control algorithm. The sensor is inserted subcutaneously and transmits data every 5 minutes to the pump via the transmitter.

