### **Reportable Adverse Events:**

For this protocol, a reportable adverse event includes any untoward medical occurrence that meets one of the following criteria, as defined below:

1. Hypoglycemia meeting the definition of severe hypoglycemia (SH)
2. Diabetic ketoacidosis (DKA)
3. A serious adverse event (SAE)
4. An adverse device effect (ADE)

Hypoglycemia and hyperglycemia not meeting the criteria below will not be recorded as adverse events unless associated with an adverse device effect (ADE). Skin reactions from sensor placement are only reportable if severe and/or if they required treatment.

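### The analysis of auto-populated correction boluses names no bolus denominator or reference, so its count of flagged adverse events cannot show whether risk after such boluses is raised

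*Combined protocol and SAP*

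**What the plan says.** The Synopsis gives the second primary safety endpoint as "The safety of the automatic population of CGM readings into the bolus calculator of the Control-IQ System". Study Objectives also places it among the primary objectives, worded as monitoring. The Study Endpoints section lists only the composite rate of severe hypoglycemia (SH) and diabetic ketoacidosis (DKA) as primary.

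The method is in the Synopsis and, almost identically, under Primary Outcome:

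- The approach is "correlating reported AEs, calculator usage data and CGM readings to understand if the bolus calculator may have caused the AE".
- The selection rule opens with the words "This analysis will isolate AEs where three consecutive CGM readings". The limits are 54 mg/dL or lower, and 250 mg/dL or higher.
- The timing condition is that this pattern "existed within five hours of receiving a correction bolus using an automatically populated CGM reading".
- Every CGM value in those five hours is to be looked at.
- Boluses with a populated value of 250 mg/dL or more "will be analyzed and evaluated separately from boluses given for lower glucose values".

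The success criterion concerns SH and DKA incidence only: "Study participants will not experience a higher incidence of SH or DKA than incidence rates reported in the literature". The exact binomial test likewise covers only SH and DKA. Determination of Sample Size promises a detailed analysis plan before the first tabulation of data; the text available here does not contain it.

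**The concern.** The question is causal, but selection starts from the outcome. The text does not say that auto-populated boluses with no event after them are counted, or how often a participant is inside a five-hour post-bolus window in ordinary time. Without one of these, a number of flagged events has nothing to be compared with.

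Two features of the filter add to this. First, the Reportable Adverse Events section says "Hypoglycemia and hyperglycemia not meeting the criteria below will not be recorded as adverse events" unless an adverse device effect is involved. Most glucose excursions after a bolus therefore cannot become cases, and the low-glucose outcome most directly tied to an over-correction is seen only when it ends in a reportable event. Second, the sensor "transmits data every 5 minutes to the pump via the transmitter", so three consecutive readings can be complete within about 15 minutes of the bolus. If the populated value was already 250 or more, the high flag can be met by the starting glucose.

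At stake is the interpretation of an endpoint that the Synopsis calls primary. A long list could be read as harm and a short one as reassurance, and neither reading would follow.

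**Working it through.** **Figure to reproduce.** The plan states no rate, threshold, test or sample size for this endpoint. The follow-up figure borrowed below does reproduce: 2,063 × (1 − 0.25) = 1,547.25, which matches the 1,547 completers in the Synopsis.

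**Inputs.**
- SH 25.35 and DKA 11.03 per 100 patient-years (Determination of Sample Size, Steps 1 and 2).
- 1,547 completers followed for 12 months, taken as 1,547 patient-years. Partial follow-up of dropouts is ignored.
- Window of five hours (Primary Outcome).
- k, auto-populated correction boluses per participant per day: **assumed**, 0.5 to 4. The documents give no frequency.
- Boluses at random times, independent of events: **assumed**, for illustration.

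**Events at benchmark rates.** SH: 1,547 × 0.2535 = 392. DKA: 1,547 × 0.1103 = 171. Together 1,547 × 0.3638 = 563.

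**Chance of being in a window.** The share of time within five hours after at least one bolus is p = 1 − exp(−5k/24). If the feature has no effect, this is also the share of events that fall in a window.

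| k per day | p | SH in a window by chance | DKA in a window by chance |
|---|---|---|---|
| 0.5 | 9.9% | 39 | 17 |
| 1 | 18.8% | 74 | 32 |
| 2 | 34.1% | 134 | 58 |
| 4 | 56.5% | 222 | 97 |

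For k from 1 to 4, 563 × 0.188 ≈ 106 to 563 × 0.565 ≈ 318 events would fall in a window. The flag also needs the CGM pattern, so these are upper figures for chance flags.

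**What one count can mean.** Suppose 74 of 392 SH events are flagged and every event in a window meets the CGM condition. The flagged share is F = 74/392.16 = 0.189, and the implied rate ratio, inside against outside windows, is [F/(1 − F)] / [p/(1 − p)]:

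- k = 0.5: 0.2326/0.1098 = 2.12
- k = 1: 0.2326/0.2317 = 1.00
- k = 2: 0.2326/0.5170 = 0.45
- k = 4: 0.2326/1.3010 = 0.18

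The same 74 cases fit a doubled rate, no association or an apparent reduction. Only bolus frequency separates them, and the plan does not say that it will be used.

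**What a reference would buy.** Compare events inside and outside windows with an exact binomial test conditional on p (two-sided 5%, 80% power), where under a rate ratio RR the inside share is p·RR/(p·RR + 1 − p). Over k = 0.5, 1, 2 and 4, the detectable RR is 1.35 to 1.57 with 392 SH events and 1.57 to 1.92 with 171 DKA events. With 39 SH events (one tenth of the benchmark, assumed) it is 2.53 to 3.53. This ignores repeated events in one participant and confounding.

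**The case against.** The other side has several good points.

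*Calculator usage data and CGM readings are named inputs, and the closing sentence on boluses populated at 250 or more can be read as a bolus-level analysis.* This stands. A reader might infer that only adverse event cases will ever be examined; the text does not establish that. What it lacks is a stated denominator, measure or comparison. The split by populated value does not supply one, because both strata are exposed.

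*Study Objectives speaks of monitoring, and the investigator judges each event's relationship to the device.* This also stands. It is tempting to say that the analysis can neither implicate nor clear the calculator, but case review can implicate individual events. It cannot estimate risk.

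*The CGM filter and the split are not useless.* Agreed. Below 250 a high flag requires a rise to that level, and the low flag stays informative in both strata. A reader might suppose that nearly every SH or DKA event meets the CGM condition whatever its cause. The documents give no figure for that, and the SH definition accepts events without a glucose measurement.

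*The numbers are hypothetical.* Correct. Corrections follow high glucose rather than arriving at random. The benchmark rates come from other therapies, and the pediatric study of this technology described in Disease background reported no SH or DKA. Step 3 expects 1,354 completers, not 1,547, which would give 1,354 × 0.3638 = 493 events. Lower event numbers shrink the counts but leave the chance share unchanged.

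*The detailed analysis plan may settle this.* It may. Nothing available does so yet, and that plan is the natural place for the fix.

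**Conclusion.** The concern holds in a limited form. For an endpoint that the Synopsis calls primary, the plan asks whether the bolus calculator may have caused adverse events, but specifies only a filter on reported events, with no bolus denominator or reference. The flagged list is useful for case review; its count cannot show whether risk after auto-populated boluses is raised. In the stratum populated at 250 or more, the high flag can also be met by glucose that was already high.

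The size is illustrative: 19% to 57% of events in a window by chance, assuming 1 to 4 auto-populated correction boluses a day at random times. The 106 to 318 events should not be read as expected counts, since they also need the benchmark rates and 1,547 patient-years.

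A reader might also infer that a self-matched comparison would isolate the feature. It would not. Corrections are given because glucose is high, so developing DKA could itself prompt more of them, and the contrast estimates the effect of a correction bolus rather than of auto-population alone.

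**What to change.** Keep the case listing and add to the detailed analysis plan, before the first tabulation:

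- **Rates with a reference.** From all uploaded calculator and CGM data, report per 1,000 auto-populated correction boluses the rate of three consecutive readings at or below 54 mg/dL, and of SH and DKA. Give them separately for populated values below 250 and at or above 250 mg/dL, with 95% confidence intervals that allow for repeated boluses in one participant. Show alongside the same rates in windows without a bolus, or after manually entered values where the usage data identify them.
- **Carry-over rule.** In the stratum at or above 250, do not count readings of 250 or more that merely continue from before the bolus.
- **Status.** Reconcile the Synopsis and Study Endpoints on whether this endpoint is primary.

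A self-matched case-crossover analysis is optional and supportive only. It must account for pre-bolus glucose, and its report should say that it does not separate auto-population from the correction bolus itself.

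Cost: analysis-plan text and extra programming on data the plan already names as inputs. Event timing is the real constraint. The adverse event form lists a date of onset, not a time, so timing must be inferred from CGM traces or an onset-time field added. The plan's own five-hour rule has the same need. Events without usable timing or CGM data cannot be assigned to a window, and their number should be reported.
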